8. PHARMACOKINETIC ASSESSMENTS

8.1. Pharmacokinetic (PK) Variable(s)

Not applicable.

8.2. Pharmacodynamic (PD) Variable(s)

Not applicable.

8.3. Biomarker and Exploratory Variable(s)

Not applicable.

9. SAFETY ASSESSMENTS

9.1. Adverse Events

All clinical AEs (defined in Section 9.3) occurring after the subject has signed the ICF and up to 4 weeks after the last dose of study medication (i.e. the follow-up period), whether observed by the investigator or reported by the subject, will be recorded on the AE eCRF page. For subjects rolled over from a preceding study (DS5565-A-E309, DS5565-A-E310, or DS5565-A-E311), any AE that is ongoing at the start of this study will be recorded as an AE in this study, and all AEs (new or from a preceding study) will be followed until resolution. For these rolled-over subjects, all AEs will be evaluated in the context of their experience in the preceding study.

All laboratory, vital sign, or ECG values should be appraised by the investigator as to clinical significance. Isolated abnormal laboratory results, vital sign findings, or ECG findings should be reported as AEs if they are symptomatic, lead to study drug discontinuation, require corrective treatment, or are otherwise defined as an adverse event of special interest (AESI) [please refer to Section 9.2].

All SAEs are to be reported according to the procedures in Section 9.4 (SAE Reporting-Procedure for Investigators). Always report the diagnosis as the AE or SAE term. When a diagnosis is unavailable, report the primary sign or symptom as the AE or SAE term with additional details included in the SAE narrative until the diagnosis becomes available. If the signs and symptoms are distinct and do not suggest a common diagnosis, report as individual entries of AE or SAE. For events that are serious due to hospitalization, the reason for hospitalization must be reported as the SAE (diagnosis or symptom requiring hospitalization). Pre-planned (prior to signing the ICF) procedures or hospitalizations for pre-existing conditions which do not worsen in severity should not be reported as SAEs (see Section 9.3 for Definitions). For deaths, the underlying or immediate cause of death should always be reported as an SAE. In addition, any serious, untoward event that may occur subsequent to the reporting period that the Investigator assesses as related to study drug should also be reported and managed as an SAE.

At each visit, the investigator should determine whether any AEs have occurred by evaluating the subject. AEs may be directly observed, reported spontaneously by the subject, or by questioning the subject at each study visit. Subjects should be questioned in a general way, without asking about the occurrence of any specific symptoms. The Investigator must assess all AEs to determine seriousness, severity, and causality, in accordance with the definitions in Section 9.3. The Investigator's assessment must be clearly documented in the site's source documentation with the Investigator's signature.

Investigators should follow subjects with AEs until the event has resolved or the condition has stabilized. Unresolved AEs, including significant abnormal laboratory values at the end of the study, should be followed up until resolution or until no longer clinically relevant.

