6.5.1.2. Visit at Week 2 of Follow-up (Visit 23; Week 54)

All subjects then will return to the clinic for post-treatment follow-up approximately 14 (\pm 3) days following the last dose of study medication.

The following activities and/or assessments will be performed at the Follow-up clinic visit (Visit 23, Week 54):

- Assess for and record AEs
- Assess for and record concomitant medication use including allowable analgesics
- Record vital signs (temperature, heart rate, supine and orthostatic blood pressure) and body weight
- Perform urine pregnancy test on all WOCBP and confirm negative
- Administer the C-SSRS(See Section 9.2.1)
- Administer the PWC

Any abnormal findings (including abnormal laboratory values) observed at the End-of-Treatment visit should be rechecked at the Follow-up visit. Further safety assessments may be required for clinically significant abnormal findings observed at the Follow-up visit.

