6.5.1.3. Telephone Contact at Week 4 of Follow-up (Visit 24; Week 56)

All subjects will be contacted by telephone approximately 4 weeks following the last dose of study medication. The following activities and/or assessments will be performed at this 4-week follow-up telephone contact:

- Assess for and record AEs
- Assess for and record concomitant medication use including allowable analgesics

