9.5. Exposure In Utero During Clinical Studies

Daiichi Sankyo must be notified of any subject who becomes pregnant while receiving or within 4 weeks of discontinuing the investigational product.

Although pregnancy is not technically an AE, all pregnancies must be followed to conclusion to determine their outcome. This information is important for both drug safety and public health concerns. It is the responsibility of the investigator, or designee, to report any pregnancy in a female subject via the Exposure in Utero (EIU) Reporting form (please contact your study monitor to receive the form). The investigator should make every effort to follow the subject until completion of the pregnancy. If the outcome of the pregnancy meets the criteria for immediate classification as a SAE (i.e. post-partum complications, spontaneous abortion, stillbirth, neonatal death, or congenital anomaly, including that in an aborted fetus), the Investigator should follow the procedures for reporting SAEs outlined in Section 9.4. Elected abortion is a procedure and should be reported following the definitions and procedures for reporting AEs or SAEs.

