17.3. Schedule of Events

Table 17.1: Schedule of Events

Study Period	Screening/Baseline (De Novo Only)			Start of Tx	on-Treatment				End of Tx/Et	Follow-Up ^a		
	1	2	3		4	5	6-11	12		13-20	21	22
Telephone Contact	--	X	--	--	--	--	--	--	--	X		X
Week	-3	-2	-1	0	1	3, 5, 7, 9, 11, 13	16	20, 24, 28, 32, 36, 40, 44, 48	52	52.5	54	56
Visit Window (Days)	--	--	--	--	±3	±3	±3	±7	±7	±1	±3	±7
Informed consent	DN			X ^b								
Inclusion/exclusion	DN			X								
Demographic information	DN			X ^b								
Medical/surgical history	DN			X ^b								
Adverse event reporting		DN	DN	X ^c	X	X	X	X	X	X	X	X
Washout instructions		DN										
Concomitant medications	DN	DN	DN	X ^c	X	X	X	X	X	X	X	X
Vital signs	DN			X ^d	X	X	X	X	X		X	
Height	DN			X ^b								
Weight	DN			X ^d	X	X	X	X	X		X	
Physical examination ^e	DN			X	X	X	X	X	X			
Fundoscopy ^e	DN							DN (V.14)	DN			
C-SSRS	DN			X ^d	X	X	X	X	X		X	
WPI/SSS	DN											

Study Period	Screening/Baseline (De Novo Only)			Start of Tx	on-Treatment				End of Tx/Et	Follow-Up ^a		
	1	2	3		4	5	6-11	12		13-20	21	22
Telephone Contact	--	X	--	--	--	--	--	--	--	X		X
Week	-3	-2	-1	0	1	3, 5, 7, 9, 11, 13	16	20, 24, 28, 32, 36, 40, 44, 48	52	52.5	54	56
Visit Window (Days)	--	--	--	--	±3	±3	±3	±7	±7	±1	±3	±7
M.I.N.I	DN											
12-lead electrocardiogram	DN			X					X			
Clinical laboratory tests	DN			X ^d	X	X	X	X	X			
Pregnancy test ^f	DN			X ^d	X	X	X	X	X		X	

Table 17.1: Schedule of Events (Continued)

Study Period	Screening/Baseline (De Novo Only)			Start of Tx	on-Treatment				End of Tx/Et	Follow-Up ^a		
	1	2	3		4	5	6-11	12		13-20	21	22
Telephone Contact	--	X	--	--	--	--	--	--	--	X		X
Week	-3	-2	-1	0	1	3, 5, 7, 9, 11, 13	16	20, 24, 28, 32, 36, 40, 44, 48	52	52.5	54	56
Visit Window (Days)	--	--	--	--	±3	±3	±3	±7	±7	±1	±3	±7
PWC										X	X	
Study drug compliance					X	X	X	X	X			
Contact IXRS	DN			X	X	X	X	X	X			
Study drug dispensing ^g				X	X	X	X	X ^h				
PGIC									X			
HADS				X					X			
EQ-5D and SF-36				X					X			
Provide daily diary			DN									
Review/collect daily diary				X ⁱ		X ⁱ		X ⁱ	X ⁱ			
Pain intensity rating				X ⁱ		X ⁱ		X ⁱ	X ⁱ			
Sleep interference score				X ⁱ		X ⁱ		X ⁱ	X ⁱ			

DN denotes visits and assessments for de novo subjects only.

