a: The follow-up period will comprise a telephone contact 3 days after the last dose, a clinic visit at 2 weeks after the last dose (Week 54 if the subject completes treatment), and a telephone contact at 4 weeks after the subject's last dose of study treatment (Week 56 if the subject completes treatment).

b: For rollover subjects, informed consent will be obtained before the start of the End-of-Tapering visit in the preceding study and demography, height, and medical history will be used from the preceding study and will not be repeated. For de novo subjects, these assessments are not applicable at Visit 4.

c: For rollover subjects, any ongoing adverse events and concomitant medications should be recorded from the preceding study

d: For rollover subjects, values for vital signs, weight, C-SSRS, clinical safety laboratory tests, and pregnancy test will be taken from the End-of-Tapering visit of the preceding study and hence will not be repeated.

- e: A full physical examination will be performed at Visit 1 (for de novo subjects) or Visit 4 (for rollover subjects) and at Visit 21 (for all subjects). An abbreviated physical examination will be performed at Visits 5 to 20. Refer to Section 9.9.2 for details. Fundoscopy (for de novo subjects) will be performed at Visit 1 (with pupil dilation) or a scanning laser ophthalmoscopy examination, Visit 14 (without pupil dilation) or a scanning laser ophthalmoscopy examination, and Visit 21 (with pupil dilation) or a scanning laser ophthalmoscopy examination.
- f: A serum pregnancy test will also be performed for all women at all clinic visits (except as noted in footnote d) through the End-of-Treatment/Early Termination visit. A urine pregnancy test will be performed for all WOCBP at the Follow-up clinic visit.
- g: Subjects receiving 15 mg QD will be dispensed a 1-month supply (1 card). Subjects receiving 15 mg BID can be dispensed every 2 weeks (1 card) or monthly (2 cards).
- h: At Visit 20 (Week 48), subjects should be instructed to take all study medication, as scheduled, up until the day of their End-of-Treatment visit (Visit 21, Week 52), but not on the morning of Visit 21 (i.e. subjects should complete dosing on the evening prior to their End-of-Treatment visit).

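### The closing safety call (Visit 24) may be made on Day 21 after the last dose, so the last week of the 4-week adverse event period may go unsolicited

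*Combined protocol and SAP*

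**What the plan says.** Section 9.1 sets the AE recording period. It starts when consent is signed and runs "up to 4 weeks after the last dose of study medication (i.e. the follow-up period), whether observed by the investigator or reported by the subject". The same section adds that a serious event after the reporting period must still be reported if the investigator judges it related to study drug.

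Section 6.5.1.3 describes the final contact: "All subjects will be contacted by telephone approximately 4 weeks following the last dose of study medication". The listed activities are AEs and concomitant medication. Footnote a of Table 17.1 ties the call to the last dose, describing it as "a telephone contact at 4 weeks after the subject's last dose of study treatment (Week 56 if the subject completes treatment").

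The window row of Table 17.1 reads "Visit Window (Days) -- -- -- -- ±3 ±3 ±3 ±7 ±7 ±1 ±3 ±7". The last entry, ±7, belongs to Visit 24 (Week 56). Nothing is scheduled after Visit 24, and no text asks for a further contact if the call is made before 4 weeks have passed.

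The preceding contact is the Visit 23 clinic visit, 14 ± 3 days after the last dose (Section 6.5.1.2). It carries the last scheduled Columbia-Suicide Severity Rating Scale (C-SSRS), the last Physician Withdrawal Checklist (PWC) and the last pregnancy test.

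**The concern.** A symmetric window suits a mid-study measurement, where a few days either way hardly matter. Visit 24 does a different job: it is the one contact at which the end of a fixed safety period can be asked about. A call in the early half of the window cannot cover days that have not yet happened.

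Section 9.1 says AEs come to light by observation, by spontaneous report, or by questioning at each visit. After Visit 24 no questioning is planned. A subject called on Day 21 is therefore asked about three weeks, and a subject called on Day 28 or later about all four. The intensity of post-treatment ascertainment then depends on when the site happened to ring.

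This matters more than usual here. Long-term safety is the primary endpoint (Section 3.1.3). Section 1.3 lists suicidal behavior and ideation, and abrupt or rapid discontinuation, among the cautions for approved drugs of the class. Section 3.1.6.1.2 reports two completed suicides in a Phase 2 study. With the C-SSRS and PWC finished at Visit 23, Visit 24 is the only later scheduled safety contact.

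**Working it through.** **Inputs**
- AE period after the last dose: 4 weeks = 28 days (Section 9.1).
- Visit 24 target: 4 weeks after the last dose, Week 56 for completers (Section 6.5.1.3; Table 17.1, footnote a).
- Visit 24 window: ±7 days (Table 17.1).
- Visit 23: 14 ± 3 days after the last dose (Section 6.5.1.2).

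Days are counted from the last dose, and a call is taken to cover events up to and including its own day.

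**The plan's own figure.** 52 + 4 = Week 56, as stated. The nominal schedule covers the 4 weeks exactly.

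**Range of compliant call days**
- Earliest: 28 − 7 = Day 21.
- Latest: 28 + 7 = Day 35.

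**Largest gap for one subject.** With a call on Day 21, Days 22 to 28 are not asked about: 28 − 21 = 7 days, and 7/28 = 25% of the period.

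**Spacing of the last two contacts.** Visit 23 at its latest is 14 + 3 = Day 17. With Visit 24 on Day 21 the contacts are 21 − 17 = 4 days apart.

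**Average gap under an assumed spread.** The documents do not say when calls will fall. Suppose each of the 15 whole-day offsets from −7 to +7 is equally likely. Offsets −7 to −1 leave 7, 6, 5, 4, 3, 2 and 1 days unsolicited; offsets 0 to +7 leave none.
- Mean: (7+6+5+4+3+2+1)/15 = 28/15 = 1.87 days per subject.
- Share of the 28 days: 1.87/28 = 6.7%.
- Share of calls made before Day 28: 7/15 = 47%.

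The mean runs from 0 days (no early calls) to 7 days (every call at the early limit).

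**With a 0/+7 window.** Calls fall on Days 28 to 35, and the unsolicited part of the 4-week period is 0 for every compliant call.

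**The case against.** The strongest reply is that nothing is lost. Section 9.1 sets the reporting period at 4 weeks and does not end it at Visit 24. An event on Day 25 in a subject called on Day 21 is inside the period and must be recorded, serious or not and related or not, if it is observed or volunteered. This is correct, and it limits the point to active solicitation. A reader might infer that the rule on related serious events governs Days 22 to 28 after an early call. It does not; it applies only after the 4 weeks.

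A reader might also infer that Visit 24 closes the pregnancy window. Section 9.5 makes notification a standing duty for "any subject who becomes pregnant while receiving or within 4 weeks of discontinuing the investigational product", with no link to Visit 24. That call lists no pregnancy item, and the last test is at Visit 23, which the ±7 days do not affect.

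Third, the named risks are measured mainly elsewhere. No C-SSRS or PWC is scheduled at Visit 24, so its window changes none of those data, and AEs already identified are followed whatever the call date. This stands: only new-onset events are affected. The treatment-emergent definition in Section 11.6.1 also makes an event three to four weeks after the last dose marginal to the main tabulations. The definition is not confined to time on drug, however, since Section 9.10.2 has post-treatment withdrawal findings reported as treatment-emergent.

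Fourth, a window centred on Day 28 gives 28 days of coverage on average. That is true of the mean, but late calls cannot offset early ones. Days 29 to 35 lie outside the required period, and they belong to different subjects.

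Finally, Section 6.5.1.3 says only approximately 4 weeks, so the window is an ordinary operational tolerance and the text does not strictly contradict itself. That is fair. The point is a mismatch between a fixed period and the contact meant to cover it.

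**Conclusion.** The concern holds as a small, inexpensive correction. A compliant Visit 24 call can fall on Day 21 with nothing scheduled afterwards. For subjects called early, new AEs on up to 7 of the 28 required days reach the database only if observed or volunteered.

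The 7-day maximum follows directly from Table 17.1 and footnote a. The mean of about 1.9 days rests on the assumed even spread of call days. Against a participation of about 56 weeks (392 days) it is 1.87/392 = 0.5%. The documents give no basis for estimating how many events would be missed.

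It would be tempting to multiply the 7-day maximum by the roughly 500 subjects the study aims to expose for 52 weeks. That would require every call to be made on the earliest allowed day, which nothing in the documents suggests. Unsolicited days are also not unobserved days.

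**What to change.** 1. In Table 17.1, change the Visit 24 window from ±7 to 0/+7 days.
2. In Section 6.5.1.3, replace the approximate timing with a statement that the call is made no earlier than 28 days after the last dose, and that AEs are asked about through Day 28.

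Footnote a already anchors the call on the last dose, so the change applies equally to completers and early discontinuers.

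The cost is one table cell and one sentence, with no extra contact. Sites keep 7 days of flexibility after Day 28 and give up the option of calling early.

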9.2. Events of Special Interest

All antiepileptic drugs carry a risk of increased suicidal behavior and ideation. Furthermore, as mentioned in Section 3.1.6, increased hepatic transaminases have been observed in the DS-5565 development program and will be treated as AESIs.

9.2.1. Suicidal Behavior and Ideation

An FDA-conducted pooled analysis of placebo-controlled clinical studies of antiepileptic drugs with varying mechanisms of actions and indications, including pregabalin and gabapentin, showed an increased risk of suicidal thoughts or behavior in subjects receiving these drugs.¹¹

The C-SSRS and MINI are to be administered at any time during the study (including unscheduled visits) where the investigator/study coordinator/site staff recognizes or become aware of (and this includes if this awareness arises during unscheduled visits or non-face-to-face communications with the patient or his/her family):

- Any suggestion of mood disturbance and/or any awareness of a potential suicidal risk,
- Substantial changes in their psychosocial environment (ie, the death of or separation of close family/friend, sudden financial burden, worsening of medical condition, etc); in this case administration of the C-SSRS/MINI and consultation with a psychiatrist (onsite preferably) should be performed.

The C-SSRS will be administered at baseline and at every clinical assessment thereafter. Based on the C-SSRS and investigator judgment, if a subject is identified as being at risk for suicide, appropriate safety measures should be implemented, including:

- A subject should be discontinued from the study, and immediately referred to a mental health professional for further evaluation, if a 'YES' response has been recorded for any question on the C-SSRS at any visit (current or past), unless the subject falls into the 'Possible Exception' category below:
 - Possible exception (applying to yes responses to C-SSRS Q1 and/or 2 only):
 1. The benefit from continuation on the study medication significantly outweighs the risk of continuing the subject on study drug. Such cases need to be discussed with the sponsor medical director and should take into account the mental health professional evaluation AND
 2. The justification for continuing the subject in the study under these circumstances is to be appropriately documented per study procedure.

Subjects should be discontinued from the clinical study and immediately referred to a mental health professional (preferably an onsite psychiatrist evaluation if possible) if subjects are assessed as having current severe or uncontrolled major depressive disorder or anxiety disorders by the MINI at any visit (current or past) and if any of the following conditions apply:

- The investigator determines that there is a suicidality risk, irrespective of any scales or
- Any “Yes” response to:
 - MINI questions
 - Module A (Major Depressive Disorder) question A3, G or
 - Any question on Module B (Suicidality) or
 - Relevant C-SSRS questions, with discontinuation criteria as outlined above.

9.2.2. Liver Enzyme Elevations/Liver Dysfunction

As described in Section 3.1.6.1.1, increases in aminotransferases have been observed in the DS-5565 development program to date. Special monitoring of such elevations during Phase 3 is described below. The Hepatic Adjudication Committee (HAC) charter includes a process by which selected cases will be adjudicated by a liver disease specialist (Section 11.10). In cases of liver laboratory abnormalities, it is important to ensure that the nature and the extent of liver injury is identified and study subjects are monitored until the liver laboratory assessments return to normal. Subjects who have any transaminase elevation associated with a clinical presentation suggestive of liver injury (i.e. including the appearance of fatigue, nausea, vomiting, right upper quadrant pain or tenderness, fever, rash, and/or eosinophilia) or an elevation of ALT or AST $\geq 3 \times$ ULN (without clinical presentation suggestive of liver injury) at any visit should be monitored closely, according to the following:

- Repeat liver tests of at least all four of the usual serum measures (ALT, AST, ALP, and total bilirubin at least 2 times weekly (the first repeat should be within 48 to 72 hours of initial abnormality) until values have decreased to $< 2 \times$ ULN, then at least every 1 or 2 weeks until resolution or return to baseline. An additional 8.5 mL serum separating tube of blood will be collected at time of event and until values return to baseline. Samples will be stored for further analysis, as required
- Review or obtain a detailed history of symptoms and prior or concurrent diseases
- Review or obtain a history of the use of concomitant drugs, including nonprescription medications, herbal and dietary supplements, alcohol, recreational drugs, and special diets
- Rule out alcoholic hepatitis; non-alcoholic steatohepatitis (NASH); hypoxic/ischemic hepatopathy; and biliary tract disease
- Obtain a history of exposure to environmental chemical agents
- Perform additional laboratory liver tests (e.g. serum lactate dehydrogenase, alkaline phosphatase, gamma-glutamyl transpeptidase, prothrombin time), evaluations for potential viral etiologies (including hepatitis A, B, C, E;

cytomegalovirus; and Epstein-Barr virus) and autoimmune etiologies (anti-nuclear antibody, anti-smooth muscle antibody, anti-mitochondrial antibody)

Combined elevations of aminotransferases and bilirubin meeting the criteria of a potential Hy's Law case [ALT or AST ≥ 3 x ULN with simultaneous total bilirubin ≥ 2 x ULN], either serious or non-serious and whether or not causally related, should always be reported to the Sponsor within 24 hours (refer to Section 9.4.1), with the investigator's assessment of seriousness, causality, and a detailed narrative. (FDA's Guidance for Industry: Drug-Induced Liver Injury: Premarketing Clinical Evaluation; July 2009; <http://www.fda.gov/downloads/Drugs/GuidanceComplianceRegulatoryInformation/Guidances/UCM072278.pdf>).¹² These events should be reported as soon as possible following the procedures outlined in Section 9.4 for SAE reporting. The sponsor will be responsible for reporting the case(s) to the FDA.

Criteria for discontinuing subjects based on transaminase increases are provided in Section 3.1.6.1.1.

For subjects discontinued from the study due to any transaminase increase or hepatic event, the following referrals should be performed:

- Gastroenterology or hepatology consultation
- Hepatobiliary ultrasound

